9.1 Definitions

9.1.1 Adverse Event

An adverse event is any untoward medical occurrence in a patient or clinical investigation subject administered a pharmaceutical product and that does not necessarily have a causal relationship with this treatment. An adverse event can therefore be any unfavorable and unintended sign (including an abnormal laboratory finding), symptom, or disease temporally associated with the use of a medicinal (investigational) product, whether or not related to the

medicinal (investigational) product. In addition, during the screening period, adverse events will be assessed regardless of the administration of a pharmaceutical product.

Adverse events will be assessed and documented, as appropriate, throughout the study (ie, after informed consent has been obtained). At each visit, the investigator will begin by querying for adverse events by asking each patient/caregiver a general, non-directed question such as "How have you been feeling since the last visit?" Directed questioning and examination will then be done as appropriate. All reported adverse events will be documented on the appropriate eCRF.

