- Missing values will not be imputed.
- Study days from the treatment day of a certain treatment cycle will be calculated as:

Study days = visit date – most recent treatment day visit date + 1.

- The study day of an event that has occurred before first treatment day will be calculated as:

Study day = date of event – treatment 1 visit date.

- Partial dates occurring when calculation of study day is germane to the study outcome will be handled as follows:

If the year is missing then the date is treated as missing.

If either the month or the day is missing, then the closest to baseline possible will be used. That is, an event occurring the year before baseline would use December and/or the last day of the month. An event occurring the year after baseline would use January and/or the first day of the month.

All partial dates will be listed “as is” in the data listings.

- All adverse events (AEs) with missing onset dates will be identified and the missing dates will be imputed as follows for analysis. These imputations are only for assigning adverse events to a particular study phase; calculations such as days to onset will not use these imputations. All partial dates will be listed “as is” in the data listings.
 - (a) For AE onset date: If day and month are missing but year is available (..../yy) then the imputed day and month will be 01/01/yy or the injection date if they have the same year, whichever is later. If day is missing but the month and year are available (mm..../yy), then the imputed day will be mm/01/yy or the injection date if they have the same month and year, whichever is later.
 - (b) For AE stop date: If day and month are missing but year is available (./.yy) then the imputed day and month will be 12/31/yy or the study exit date if they have the same year, whichever is earlier. If day is missing but the month and year are available (mm./.yy), then the imputed day will be the last day of the month mm in the year yy or the study exit date if they have the same month and year, whichever is earlier.

- (c) If the AE onset or stop month, day, and year are missing (..../..), then the study entry date will be used as the AE onset date and the exit date will be used as the AE stop date.

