6.2 Treatment Emergent Adverse Events

Adverse events are collected for the period prior to the first treatment (which are referred to as pre-treatment AEs as cited in Section [Error! Reference source not found.](#)) and for the period on or after the first treatment.

An overall treatment-emergent adverse event (TEAE) is an adverse event with onset on or after the initiation of the first treatment or an adverse event with onset prior to the first treatment that worsened in severity or became serious on or after the initiation of the first treatment.

A treatment cycle treatment-emergent adverse event (TEAE) is an adverse event with onset on or after the initiation of the cycle treatment but before the initiation of the next cycle treatment or an adverse event with onset prior to the cycle treatment that worsened in severity or became serious on or after the initiation of the cycle treatment but before the initiation of the next cycle treatment.

An AE that stops during certain treatment cycle and recurs in the subsequent treatment cycle(s) is considered as a TEAE in the subsequent treatment cycle(s) if it fulfills the TEAE definition above.

The number and percentage of patients reporting each event will be summarized by treatment cycle and overall as follows:

- i. By primary SOC and preferred term. At each level of summarization (overall, primary SOC, and preferred term) a patient will be counted once if he/she reports 1 or more experiences at that level.
- ii. By primary SOC, preferred term and severity. For a given adverse event of a patient, if more than 1 severity grade was reported, the worst severity grade will be included in the tabulation.

An overall summary of TEAE will be presented. In addition, individual patient data listings (including adverse event listings that include the investigator verbatim terms and MedDRA lower level terms) will be provided.

Furthermore, the assessment of possible distant spread of toxin will be performed using the list of 39 MedDRA preferred terms (version 19.0 or its updated version as appropriate during the time of data analysis).

MedDRA Preferred Terms Evaluated for Possible Distant Spread of Toxin

Cardiac Disorders

Bradycardia

Eye Disorders

Accommodation disorder
Diplopia
Extraocular muscles paresis
Eyelid function disorder
Eyelid ptosis
Pupillary reflex impaired
Vision blurred

Gastrointestinal Disorders

Constipation
Dry mouth
Dysphagia
Ileus paralytic

Infections and Infestations

Botulism

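### SAP 2.3 rule (c) dates a wholly undated AE at an undefined study entry date with no injection-date floor, so a de novo patient's on-treatment AE may be classed as pre-treatment

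*SAP*

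**What the plan says.** SAP 2.3 (Data Conventions) has three imputation rules for AE dates, introduced as applying to AEs whose onset date is missing. It gives their purpose: "These imputations are only for assigning adverse events to a particular study phase". Days to onset are not computed from imputed dates, and the listings show partial dates unaltered.

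- **Rule (a), partial onset.** With only the year known, the onset becomes "01/01/yy or the injection date if they have the same year, whichever is later". A matching rule covers a known month and year.
- **Rule (b), partial stop date.** The end of the known period is used, capped at study exit.
- **Rule (c), date wholly missing.** The trigger reads "If the AE onset or stop month, day, and year are missing". Both dates are then filled in. The instruction for onset is "then the study entry date will be used as the AE onset date"; for the stop, the rule takes study exit.

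SAP 6.2 then divides AEs at the first treatment: "An overall treatment-emergent adverse event (TEAE) is an adverse event with onset on or after the initiation of the first treatment". An earlier AE also qualifies if it worsened or turned serious after treatment. A separate pre-treatment category exists: "Adverse events are collected for the period prior to the first treatment".

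On when the study begins for AE purposes, Protocol 9.1.1 says: "Adverse events will be assessed and documented, as appropriate, throughout the study (ie, after informed consent has been obtained". Protocol 9.3 likewise starts the SAE reporting period at consent. Under Protocol 5.3, de novo patients sign consent at a screening visit, while IVRS/IWRS enrolment takes place at day 1 for both patient types.

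**The concern.** The imputed date decides whether an AE is treatment-emergent. Rule (a) never places an AE before the injection when the known year or month is that of the injection. Rule (c) has no such floor, so the AE with the least information can receive the less cautious handling.

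Whether it does depends on a term that the visible SAP leaves undefined. If study entry is consent or screening, it precedes the first injection for de novo patients, and their wholly undated on-treatment AEs fall out of the TEAE numerator. Two programmers could then produce different TEAE tables from the same data. The study's objective is long-term safety, and under the screening reading the error understates AE incidence.

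The second problem is the trigger. By joining onset and stop with *or*, rule (c) can apply to an AE that rule (a) already handles, and it imputes both dates whichever one is missing.

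**Working it through.** The plan states no figure on this point, so there is none to reproduce. The check is of the date logic.

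**1. Where does a wholly undated AE land?**

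Inputs: five treatments 12 weeks apart (Protocol 3), so at 0, 84, 168, 252 and 336 days after treatment 1. Assume a de novo patient with a true onset 10 days after treatment 3, at 168 + 10 = 178 days (cycle 3), and no recorded date. The gap g from study entry to treatment 1 is not in the visible text; values of 1, 7 and 28 days are assumed, and 0 represents entry at day 1. Rule (c) gives onset = −g. A floor at the first injection gives onset = max(−g, 0) = 0.

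| Study entry | Onset under rule (c) | Phase under SAP 6.2 | Phase with the floor |
|---|---|---|---|
| 1 day before treatment 1 | −1 | pre-treatment | TEAE, cycle 1 |
| 7 days before | −7 | pre-treatment | TEAE, cycle 1 |
| 28 days before | −28 | pre-treatment | TEAE, cycle 1 |
| Day 1 | 0 | TEAE, cycle 1 | TEAE, cycle 1 |

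For comparison, suppose only the year is known and it is the year of the first injection. Taking that injection as the one meant, rule (a) gives the later of 1 January and the injection date, which is the injection date: a cycle 1 TEAE. In every row the true cycle is 3, so the floor restores the AE to the overall table but not to its true cycle.

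Rollover patients have no such gap, because Protocol 3 makes the exit visit of Study 191622-111 their day 1.

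**2. How large could the effect be?**

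The documents give no count of undated AEs. For an assumed k patients lost from one table row, the change is 100 × k / 350 percentage points:

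- k = 1: 100 / 350 = 0.29
- k = 3: 300 / 350 = 0.86
- k = 5: 500 / 350 = 1.43
- k = 10: 1000 / 350 = 2.86

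Here k counts patients, not events. SAP 6.2 counts a patient once per level, so losing an event changes a row only if it was that patient's only event there. In a Placebo/BTX column, where SAP 2.3 places all de novo patients, the denominator is smaller and the same k weighs more.

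**3. What does the trigger reach?**

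| Onset | Stop | Result |
|---|---|---|
| Fully known | Wholly missing | Outside the rules' scope; onset unchanged |
| Partly known | Wholly missing (eg, ongoing) | Rule (a) and rule (c) give different onsets |
| Wholly missing | Known | Read literally, the known stop date becomes the exit date |
| Wholly missing | Wholly missing | Onset = study entry, stop = exit |

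The third row matters because a known stop date before the first injection is the one fact that would show the AE to be pre-treatment. Even on the day 1 reading, such an AE would be given a day 1 onset and counted as a TEAE.

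**The case against.** The strongest reply is that study entry may mean day 1. Protocol 5.3 enrols patients in the IVRS/IWRS at day 1. Protocol 4.5.1 and 4.5.2 give much the same stable-dose instruction, one for patients on these drugs at day 1 and the other for patients entering the study on them. Study weeks are counted from day 1. On that reading no on-treatment AE is lost. This stands as a fair alternative, but Protocol 9.1.1 and 9.3 tie AE and SAE collection to consent, so the question is not settled. A definition may also lie in removed SAP text, which is why the point is confined to what is visible.

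The effect is also likely to be small. Rule (c) needs even the year to be missing, AEs are queried at every visit, and data are cleaned before lock. Affected AEs stay in the listings, and those that worsen or become serious return as TEAEs. All of this stands.

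Three stronger inferences are tempting but unsupported:

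- **That every ongoing AE has its known onset overwritten.** The lead-in limits the rules to AEs with a missing onset date, so a fully recorded onset is safe.
- **That TEAE incidence is the trial's only objective.** The objective is long-term safety. AE incidence is one of several safety variables, and the others are redacted.
- **That a de novo versus rollover comparison is biased.** No such comparison is visible. De novo patients are grouped with placebo rollovers, and Protocol 7.3 plans no hypothesis testing unless otherwise specified.

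**Conclusion.** The point holds as a gap in definition and drafting, not as a demonstrated bias. Rule (c) relies on an undefined date and lacks rule (a)'s floor. Under the consent or screening reading, a de novo patient's wholly undated on-treatment AE is removed from the TEAE tables unless it worsened or became serious. Under the day 1 reading it is kept, in cycle 1. For each such event the overall classification is all or nothing; the total effect is unknown and probably small. The figures of 0.29 to 2.86 percentage points rest on an assumed 1 to 10 patients and all 350 as denominator. The trigger's conflict with rule (a) for a partly dated onset, and its literal replacement of a known stop date, follow from the wording under either reading. Correction is worthwhile because the possible error is anti-conservative in a safety study and costs little to remove.

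**What to change.** Replace rule (c) in SAP 2.3 with separate rules:

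1. If onset is wholly missing, set it to the date of the first Study 191622-112 injection. If a known stop date is before that injection, class the AE as pre-treatment.
2. If the stop date is wholly missing, set only the stop date, to the exit date, and keep the recorded onset or the one from rule (a).
3. Never overwrite a recorded date.

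Report the number of AEs with an imputed onset alongside the TEAE tables. Merely defining study entry as day 1 would prevent the loss but leave the trigger unresolved.

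The cost is a few sentences and a small programming change. Some true screening-period AEs may be counted as TEAEs, which is the cautious direction. Wholly undated AEs will all fall in cycle 1, so the per-cycle tables may still misplace them; the reported count shows how far that matters.

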3.1 Disposition and Exit Status

A patient disposition and exit status table will be done for the mITT population. A cumulative frequency table showing patient disposition (enrolled, completed, and discontinued) in the study with sub-categorization by reason of premature discontinuation for each treatment group and overall patients will be generated.

4. Demographics and Other Baseline Characteristics

4.1 Demographics

Demographics data will be analyzed using the mITT population. Age, race, sex will be summarized using frequency tabulations and/or summary statistics, both by treatment group and overall patients. Race will be classified as White and non-White (black, Asian, Hispanic, and other). In addition, race will be displayed as collected in the CRF (White, black, Asian, Hispanic, and other). Age will also be summarized by ≤ 6 and > 6 years of age groups.

4.2 Concomitant Medications

Using the mITT population, the number and percent of patients who take concomitant medication (as defined in Section 2.3) will be presented by treatment group and overall patients for the base preferred (drug) name according to the World Health Organization Drug Dictionary Enhanced (WHO DDE) with the same active ingredients by the primary system organ class (SOC) and preferred term of the MedDRA code.

5. Efficacy Analyses

5.1 Collection of Primary Efficacy Measurement(s) and Derivation of Primary Efficacy Variable(s)

No primary efficacy variable is identified.

[figure not shown]
5.2 Primary Efficacy Analyses

Not applicable.

5.3 Secondary Efficacy Analyses

Not applicable.

[REDACTED]

[REDACTED] [REDACTED]
[REDACTED]
[REDACTED]

[REDACTED]
[REDACTED]

6. Safety Analyses

Safety variables including the incidence of adverse events, [REDACTED]

[REDACTED]
[REDACTED]
[REDACTED]

[REDACTED]
[REDACTED]
[REDACTED]

[REDACTED]
[REDACTED]
[REDACTED]
[REDACTED]
[REDACTED]

[REDACTED]
[REDACTED]
[REDACTED]

[REDACTED]
[REDACTED]

6.2 Treatment Emergent Adverse Events

Adverse events are collected for the period prior to the first treatment (which are referred to as pre-treatment AEs as cited in Section [Error! Reference source not found.](#)) and for the period on or after the first treatment.

An overall treatment-emergent adverse event (TEAE) is an adverse event with onset on or after the initiation of the first treatment or an adverse event with onset prior to the first treatment that worsened in severity or became serious on or after the initiation of the first treatment.

A treatment cycle treatment-emergent adverse event (TEAE) is an adverse event with onset on or after the initiation of the cycle treatment but before the initiation of the next cycle treatment or an adverse event with onset prior to the cycle treatment that worsened in severity or became serious on or after the initiation of the cycle treatment but before the initiation of the next cycle treatment.

An AE that stops during certain treatment cycle and recurs in the subsequent treatment cycle(s) is considered as a TEAE in the subsequent treatment cycle(s) if it fulfills the TEAE definition above.

The number and percentage of patients reporting each event will be summarized by treatment cycle and overall as follows:

- i. By primary SOC and preferred term. At each level of summarization (overall, primary SOC, and preferred term) a patient will be counted once if he/she reports 1 or more experiences at that level.
- ii. By primary SOC, preferred term and severity. For a given adverse event of a patient, if more than 1 severity grade was reported, the worst severity grade will be included in the tabulation.

An overall summary of TEAE will be presented. In addition, individual patient data listings (including adverse event listings that include the investigator verbatim terms and MedDRA lower level terms) will be provided.

Furthermore, the assessment of possible distant spread of toxin will be performed using the list of 39 MedDRA preferred terms (version 19.0 or its updated version as appropriate during the time of data analysis).

MedDRA Preferred Terms Evaluated for Possible Distant Spread of Toxin

Cardiac Disorders

Bradycardia

Eye Disorders

Accommodation disorder
Diplopia
Extraocular muscles paresis
Eyelid function disorder
Eyelid ptosis
Pupillary reflex impaired
Vision blurred

Gastrointestinal Disorders

Constipation
Dry mouth
Dysphagia
Ileus paralytic

Infections and Infestations

Botulism

Musculoskeletal and Connective Tissue Disorders

Muscular weakness

Nervous System Disorders

Bulbar palsy
Cranial nerve palsies multiple
Cranial nerve paralysis
Dysarthria
Facial paralysis
Facial paresis
Hyporeflexia
Hypotonia
Paralysis
Paresis cranial nerve
Peripheral nerve palsy
Peripheral paralysis
Speech disorder
Vocal cord paralysis
Vocal cord paresis

Renal and Urinary Disorders

Urinary retention

Respiratory, Thoracic and Mediastinal Disorders

Aspiration
Diaphragmatic paralysis
Dysphonia
Dyspnoea
Pneumonia aspiration
Respiratory arrest
Respiratory depression
Respiratory failure

Reproductive System and Breast Disorders

Pelvic floor muscle weakness

Study 191622-112 Analysis Plan
GDD-BSP-T-001 v2012.5

7. Interim Analyses

Periodic safety summaries will be provided to the SDRC for review. In addition, periodic safety and efficacy data summaries may be generated for the purpose of study monitoring. An interim safety analysis may be performed for regulatory filing, if needed.

8. Pharmacokinetic Data Analyses

There will be no pharmacokinetic data to be analyzed from this study.

9. Health Outcomes Data Analyses

There will be no health outcomes data to be analyzed from this study.

10. Data Collected but not Analyzed

The date and signature of investigator and system required variables of electronic data capture (EDC) and IVRS/IWRS will not be analyzed.

11. Deviations from Protocol

There is no deviations from the protocol amendment 3.

ALLERGAN

Analysis Plan 191622-112

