7.3.2 Safety Analyses

Safety variables including the incidence of adverse events, [REDACTED]

[REDACTED]

[REDACTED]

[REDACTED]

[REDACTED]

[REDACTED]

[REDACTED]

The incidence of adverse events will be tabulated by primary system organ class and the preferred term overall and for each treatment cycle. [REDACTED]

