7.4 Subgroup Analyses

[figure not shown]
The safety analyses for all adverse events will be presented by age, previous exposure to botulinum toxin, and type of anesthesia, if appropriate.

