2.3 Data Conventions

The data conventions and definitions listed in this section are to be applied to all analyses unless stated otherwise in a subsequent section of this Analysis Plan.

- Data will be analyzed according to the following treatment groups:
 - For rollover patients from Study 191622-111 under treatment group BTX 4 U/kg, BTX 8 U/kg, or Placebo, their corresponding treatment group will be

designated as BTX 4 U/kg/BTX, BTX 8 U/kg/BTX, Placebo/BTX, respectively.

- For de novo patients, , their treatment group will be designated as Placebo/BTX.
- Concurrent medication and prior medication will be calculated using the following convention: 1) If the stop date of taking medication is prior to first injection date, then it will be counted as prior medication; 2) If the start date of taking medication is after or on first injection date, then it will be counted as concomitant medication; 3) If the start date of taking medication is prior to first injection date and stop date is on or after last injection date, then it will be counted as both prior medication and concomitant medication.
- Concurrent procedures are defined as those taken on or after the first injection date.
- All data will be listed with the exceptions of commonly expected results such as physical examination, pregnancy tests results for females when not applicable, etc.
- Summary statistics of continuous variables will include the sample size (N), mean, standard deviation, median, minimum (Min), and maximum (Max).
- Summary statistics of categorical variables will include the sample size (N) and/or frequency counts and percentages.
- Medical Dictionary for Regulatory Activities (MedDRA) nomenclature will be used to code all adverse events (AEs) and medical history.
- World Health Organization Drug Dictionary Enhanced (WHO DDE) preferred name and MedDRA will be used to code all medications.
- Metric systems will be used for all applicable measures including (kg), height (cm), and clinical laboratory data (SI: Standard International units).
- Baseline is defined as the last non-missing observation prior to receiving the first treatment for de novo patients and the same baseline in study 191622-111 for the rollover patients. For some measurements not measured in study 191622-111, the last non-missing observation prior to receiving the first treatment in study 191622-112 will be used. Change from baseline is calculated as follow-up minus baseline value.

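### Does tabulating adverse events by cycle and overall leave the plan without a needed safety summary for sessions above 8 U/kg?

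*SAP*

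**What the plan says.** SAP 6.2 gives the axes of the treatment-emergent adverse event tables: "The number and percentage of patients reporting each event will be summarized by treatment cycle and overall as follows". They are broken down by system organ class and preferred term, and again with severity. Protocol 7.3.2 agrees: "The incidence of adverse events will be tabulated by primary system organ class and the preferred term overall and for each treatment cycle". Protocol 7.4 adds subgroups: "The safety analyses for all adverse events will be presented by age, previous exposure to botulinum toxin, and type of anesthesia, if appropriate".

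For toxin effects away from the injection site, SAP 6.2 says "the assessment of possible distant spread of toxin will be performed using the list of 39 MedDRA preferred terms", with no visible grouping. It also promises that "individual patient data listings (including adverse event listings that include the investigator verbatim terms and MedDRA lower level terms) will be provided". SAP 2.3 adds: "All data will be listed with the exceptions of commonly expected results".

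SAP 2.3 also sets default groups for all analyses. Rollover patients keep their Study 191622-111 arm and are "designated as BTX 4 U/kg/BTX, BTX 8 U/kg/BTX, Placebo/BTX, respectively". For de novo patients, "their treatment group will be designated as Placebo/BTX".

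On dose, the Protocol Summary and Protocol 5.4.1 cap cycle 1 at 8 U/kg (300 U). Protocol 5.4.3 has two ceilings for cycles 2 to 5: 8 U/kg (300 U) for a single limb, and 10 U/kg (340 U) for both lower limbs in diplegic patients or for upper and lower limbs combined. The investigator chooses the dose below the ceiling.

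**The concern.** Safety is the study's only objective, and the clinical hypothesis in Protocol 2.2 names the 8 U/kg and 10 U/kg regimens separately. The protocol also supports them differently. In Protocol 1.4, 8 U/kg matches the top dose group of Study 191622-111. The sponsor trials in Protocol 1.3.1 with a stated dose used 4 to 8 U/kg, and the case for 10 U/kg rests on published guidance and toxicology. A reader would therefore want to see what happened in the sessions above 8 U/kg.

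None of the visible axes isolates those sessions. Cycles 2 to 5 each mix both ceilings. The SAP 2.3 groups carry dose labels, but these describe the previous trial: a de novo patient due to receive 8 U/kg in cycle 1 is labelled Placebo/BTX. The subgroups in Protocol 7.4 are unrelated to dose. If distant-spread events were more frequent above 8 U/kg, a pooled row could understate them, and the reader would have to rebuild the rate from listings.

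**Working it through.** There is no planned figure to reproduce. The sample size of about 350 was set empirically, and Protocol 7.3 plans no hypothesis testing unless otherwise specified. The check has four parts.

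**1. Do the two ceilings really differ?** The maximum dose at rounded weight w (Protocol 5.4.4) is min(8w, 300) for one limb and min(10w, 340) for several.

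| Dosing weight | One limb | Several limbs |
|---|---|---|
| 34 kg | 272 U (8.00 U/kg) | 340 U (10.00 U/kg) |
| 38 kg | 300 U (7.89) | 340 U (8.95) |
| 42 kg | 300 U (7.14) | 340 U (8.10) |
| 43 kg | 300 U (6.98) | 340 U (7.91) |

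The ceilings differ at every weight, but a dose above 8 U/kg is possible only at 42 kg or less.

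**2. How many sessions could be affected?** At most 350 × 5 = 1,750 sessions take place, of which 350 × 4 = 1,400 (80%) are in cycles 2 to 5. This is only an upper bound:
- Five treatments fit only if every interval stays at the 12-week minimum (4 × 12 = 48, the last week for retreatment).
- Monoplegic patients are eligible and would ordinarily have one limb to treat.
- Patients at 43 kg or more cannot exceed 8 U/kg.

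The documents do not give the share actually above 8 U/kg.

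**3. What would pooling hide?** This can only be illustrated. Assume 1% of patients have an event in a cycle at 8 U/kg or less and 3% above it, with 10%, 20% or 50% of 350 patients above:
- 10%: 315 × 0.01 + 35 × 0.03 = 4.2; 4.2/350 = 1.2%
- 20%: 280 × 0.01 + 70 × 0.03 = 4.9; 4.9/350 = 1.4%
- 50%: 175 × 0.01 + 175 × 0.03 = 7.0; 7.0/350 = 2.0%

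A separate row would be imprecise. With zero events, the exact two-sided 95% upper limit is 1 − 0.025^(1/n): 10.0% for n = 35, 5.1% for 70 and 2.1% for 175, against 1.05% for 350. The rates and shares are all assumed, so none of this measures a fault in the plan.

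**4. Can the table be called missing?** No, for three reasons:
- SAP section 6 is blacked out directly after it begins to list the safety variables. Protocol 7.3.2 is blacked out on both sides of its visible adverse event sentence, and a figure is missing just before the sentence in Protocol 7.4.
- SAP 6.1 is not visible. The SAP contents list puts 6.2 on page 13 and section 7 on page 19. The visible 6.2 is about a page of text plus a 39-term list, which is unlikely to fill six pages.
- Protocol 10.7 has blood taken for hematology, chemistry, HbA1c and immunogenicity. No analysis of these is visible in SAP 6, yet SAP 10 lists only the investigator's date and signature and system variables as collected but not analysed. Section 6 therefore very likely contains safety displays that cannot be seen. Dose is likewise not on the SAP 10 list.

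So the documents cannot show whether a by-dose or by-limb summary exists.

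**The case for a change.** The best argument for the concern is that it does not need to call the plan deficient. No visible table separates the regimens that the hypothesis names. Dose and weight are recorded at each treatment, so a descriptive split costs little. Listings allow the rates to be rebuilt, but they are not a planned summary. The toxicology in Protocol 1.4 is itself reported by dose and, in the repeated-dose monkey studies, by number of injection sites. All of this is accurate, and asking the sponsor what the hidden text contains would be reasonable.

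It still does not amount to a fault. The hypothesis in Protocol 2.2 is one statement about acceptable safety up to the permitted maxima, not a comparison of regimens. Incidence overall and by cycle answers it. Nor is it clear that the new information lies mainly above 8 U/kg: the only multiple-treatment study in Protocol 1.3.1 with a stated dose used 4 U/kg, so repeated treatment at 8 U/kg is also new relative to those trials.

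The obvious extra table has a weakness of its own. Doses above 8 U/kg can occur only in cycles 2 to 5, so a class of 8 U/kg or less across all cycles would take in every cycle 1 session. Suppose all 1,750 sessions took place and 10%, 20% or 50% of the 1,400 later ones were above 8 U/kg. Cycle 1 would then make up 350/1,610 = 22%, 350/1,470 = 24% or 350/1,050 = 33% of the lower class, and none of the upper. Dose would be confounded with cycle order and cumulative exposure. It would also be confounded with body weight, with topography (10 U/kg in both lower limbs is for diplegic patients only) and with selection for retreatment.

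**Conclusion.** The concern does not hold. Followed as written, the visible plan gives correct descriptive incidence for the sole objective: overall, by cycle with cycle 1 kept apart, and with patient listings behind it. No number, rule or definition in it is wrong, and no planned estimate is biased for the quantity it describes.

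What remains is a wish for an additional non-randomised table. Its value depends on the share of patients above 8 U/kg and on event rates that the documents do not give. The conclusion rests on two points: text hidden by redaction cannot be counted as absent from the plan, and Protocol 2.2 is read as one statement about safety up to the maxima. If the hidden text turned out to hold no by-regimen summary, this would still be a choice of descriptive presentation, with the rates recoverable from the listings.
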